4. STUDY ENROLLMENT AND WITHDRAWAL

4.1. Inclusion criteria

- Diagnosis of PRP by clinical assessment and biopsy.
- Male subject age 18-99, willing to use a reliable form of birth control if sexually active with a woman who is able to become pregnant.
- Female subject age 18-99; either of non-childbearing potential or of childbearing potential who test negative for pregnancy and agree to use a reliable method of birth control or remain abstinent during the study and for at least 12 weeks following the last dose of guselkumab.
- Involved BSA ≥ 10% at baseline.
- Are a candidate for phototherapy and/or systemic therapy.
- Willingness to travel to OHSU for all study visits, or willing/able to participate in remote videoconferencing visits with access to a computer with internet capabilities and webcam.
- Have given written informed consent approved by the OHSU Investigational Review Board.

4.2. Exclusion criteria

- Known malignancy or lymphoproliferative disease (except treated basal cell skin cancer, treated squamous cell skin cancer, or treated cervical carcinoma in situ) for at least 5 years.
- Active, untreated, acute or chronic infection, or immunocompromised to an extent that such that participation in the study would pose an unacceptable risk to the subject.
- Positive for human immunodeficiency virus, hepatitis B virus, or hepatitis C virus.
- Have latent or active untreated tuberculosis (TB), a positive QuantiFERON-TB Gold test result, signs or symptoms of active TB on medical history or physical examination, or close contact with a person with active TB and have not undergone evaluation or treatment for TB. Those who are currently undergoing treatment or who have documented completed treatment for active or latent TB without re-exposures will not be excluded.
- Previous treatment with any agent that targets the interleukin 23 p19 subunit specifically.
- Systemic treatment with prednisone in the last 2 weeks, or other systemic therapies or phototherapy for PRP within the past 4 weeks or 5 half-lives prior to baseline, whichever is longer. For biologic therapies, the specific washout periods used will be: etanercept <28 days; infliximab, adalimumab, ixekizumab, or alefacept <60 days; golimumab <90 days; secukinumab <5 months; ustekinumab <8 months; rituximab or efalizumab <12 months.
- Have a known allergy or hypersensitivity to any biologic therapy that would pose an unacceptable risk to the subject if participating in this study.
- Have or intend to have a live vaccine within 3 months prior to baseline or 12 months prior to baseline in the case of the BCG vaccine, or any live vaccine during the course of study or within 3 months after the last administration of study drug.
- Had any major surgery within 8 weeks prior to baseline or will require major surgery during the study that, in the opinion of the investigator, would pose an unacceptable risk to the subject.
- Presence of significant uncontrolled cerebrovascular, respiratory, hepatic, renal, gastrointestinal, endocrine, hematologic, neurologic, or neuropsychiatric disorders, or abnormal laboratory screening values that, in the opinion of the investigator, pose an unacceptable risk to the subject if participating in the study or of interfering with the interpretation of the data.
- Have clinical laboratory test results at screening that are outside the normal reference range of the population and are considered clinically significant, or have any of the following specific abnormalities: Neutrophil count <1500 cells/µL, white blood cell count <3500 cells/µL, platelet count <100,000 cells/µL, AST or ALT or alkaline phosphatase > 2 times the upper limit of normal, hemoglobin <10 g/dL, serum creatinine >1.5 mg/dL. A single retest of laboratory values is permitted if one or more values is out of range.
- Women who are lactating or breastfeeding.
- Have any other condition that precludes the subject from following and completing the protocol, in the opinion of the investigator.
- Are investigator site personnel directly affiliated with this study and/or their immediate families (spouse, parent, child, or sibling).

• Are currently enrolled in, or discontinued from a clinical trial involving an investigational product or non-approved use of a drug or device within the last 4 weeks or a period of at least 5 half-lives of the last administration of the drug, whichever is longer, or concurrently enrolled in any other type of medical research judged not to be scientifically or medically compatible with this study.

4.3. Recruitment and Identification of Participants

The trial will recruit subjects with moderate-to-severe PRP, either newly diagnosed or failing other therapies due to side effects or lack of efficacy. A number of recruitment strategies will be utilized for this study proven to be effective by our group in previous studies.

- OHSU and community dermatology clinics
- OHSU OCTRI Cohort Discovery tool to identify patients with PRP via Epic, and a phone call to those patients
- Publicity on the PRP Support Group Facebook page with prior approval of Facebook page manager
- Publicity through the PRP Alliance patient advocacy organization, including an email to members of the PRP Alliance, following prior approval from listserv manager
- Research Match
- Letters mailed to physicians outside of OHSU

4.4. Vulnerable Populations

Children, neonates, pregnant women, prisoners, and decisionally impaired adults will not be enrolled in the study.

5. STUDY PROCEDURES, EVALUATIONS, AND SCHEDULE

5.1 Study Visit Procedures

5.1.1 Pre-trial

During the first contact with the study team, an overview of the trial will be given. Because of the rarity of PRP, subjects may be traveling from distant locations for the study; thus the phone script is intended to be somewhat more comprehensive for a subject to determine if they are interested and able to participate. If they would like to participate, a request for information will be signed by the subject and sent to the subject's healthcare providers to review records pertinent to the diagnosis of PRP. Once the study investigator has reviewed the records and confirmed that a diagnosis of PRP has been made by a qualified healthcare provider, an appointment for a screening visit will be made. For subjects in whom the screening visit will be completed by telemedicine, the informed consent form will be emailed or mailed to the subject prior to the screening visit.

5.1.2. Screening

Subjects will read the informed consent form and all questions about the study will be answered by a study investigator and research staff. Screening questions will be asked and eligibility will be determined by qualified research staff. Subjects will be asked about vaccine history to ensure that recommended vaccines are up to date, and subjects will be reminded that live vaccines (such as the intranasal influenza vaccine, BCG vaccine, or live varicella zoster vaccine (Zostavax)) are not permitted during the study. Contraception method will also be recorded. An investigator will perform an assessment of BSA to calculate disease severity. If all other criteria are met, a blood sample will be drawn to screen for pregnancy (in female subjects), HBV, HCV, HIV, and QuantiFERON gold for tuberculosis, and to check CBC and CMP. If subjects have had HBV, HCV, HIV, and tuberculosis testing within 3 months prior to screening, records of these results will be sufficient and the tests will not be repeated. PPD skin testing may be used if blood testing for tuberculosis is unavailable.

For interested subjects, the screening visit may be performed via secure video-conferencing using the OHSU Nexus (Cisco Meeting) app, in which case the study consent will be reviewed during the telemedicine videoconference. Eligible subjects willing to proceed with treatment will be asked to document consent via e-consent in REDCap, or signed written consent emailed or faxed to the investigators. Following receipt of signed consent, a screening blood draw will be performed at the lab of the subject's choice and results will be sent to the investigators.

Upon confirmation of normal blood tests as defined in the exclusion criteriasubjects will be scheduled for enrollment and Visit 1 as appropriate for any medication washout period required in the exclusion criteria. If blood tests are abnormal, the subject will be informed and referred to her or his primary care physician for assessment.

For Spanish-speaking subjects, the English-written consent form will be verbally translated with the help of a Spanish interpreter. All questions regarding the study will be translated to study staff and answered to patient satisfaction. Subjects will then be provided the adapted boilerplate consent, "Consent Form – Short – Spanish," to sign. A copy of both signed consents will be provided to the patient and uploaded in the patient's chart.

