5.1.3. Enrollment

The inclusion/exclusion criteria will be re-reviewed and subjects may proceed with visit 1 on the same day if they continue to meet criteria.

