5.1.4. Visit 1 / Week-0 (baseline)

Visit 1 will be performed at OHSU for all subjects.

- Study personnel will gather the following information from the subjects and record the results in REDCap:
 - Demographics (sex, gender, race, ethnicity)
 - Current medications
 - Drug allergies
 - Use of alcohol, tobacco, and other substances
 - PRP medical history
 - General medical history and adverse events since screening
 - Family medical history
 - Review of Systems
 - Height and weight
 - Blood pressure
 - Pulse
- Subjects will enter the following information about their disease and medical history via OHSU REDCap survey:
 - DLQI
 - PSSD
 - iPRPASI
- The subject will be clinically examined by an investigator (clinician or research nurse) who will assess the following and record the results in OHSU REDCap:
 - Full body skin exam with documentation of PASI, PGA, PPPGA, and NAPSI
 - Examination of the oral mucosa
 - Heart and lung auscultation
 - Palpation of the cervical, axillary, and inguinal lymph nodes
 - Presence of peripheral edema
- Photographs will be taken using a high-resolution digital camera of all body regions against a dark backdrop to visually record extent of disease. Subjects will assume standardized poses according to published recommendations (*31*), with the addition of focused photographs of the palms and nails.
- Subjects will undergo a punch biopsy (consisting of three adjacent 3 mm punch biopsies, a total surface area equivalent to the size of a 5 mm punch biopsy) from affected skin, performed by an

investigator. One additional 3 mm punch biopsy will be obtained from non-lesional skin as a control if non-lesional skin is available. For consistency, skin of back will be chosen for biopsy if an affected site is available. If back skin is not available, alternate sites in order of preference will include: chest, arm, leg. Location of the biopsy will be carefully documented.

- Blood will be drawn for measuring levels of inflammation
- A saliva sample will be collected for genetic analysis
- The first dose of 100 mg of subcutaneous guselkumab will be administered by trained study personnel while the study subject undergoes teaching for future self-administration.
- Subjects who plan to complete future visits by videoconferencing will receive a scale and sphygmomanometer for future vital sign assessments

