5.4. Table 1: Study Schedule of Events

*Visit optionally to be performed via secure telemedicine videoconferencing for subjects >30 miles from Oregon Health & Science University. ***Guselkumab subcutaneous dose: 100mg on W0, W4, W12, W20. ****Laboratory studies will include: CBC and CMP at screening, W4, W12, and W20 as well as HBV, HCV, HIV, tuberculosis, and pregnancy (for females if childbearing potential) at screening.

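### The plan requires no pregnancy test at Visit 1 and sets no limit on the age of the screening test, so a first dose can be given on an outdated negative result

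*Combined protocol and SAP*

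**What the plan says.** Section 4.1 admits women of childbearing potential "who test negative for pregnancy and agree to use a reliable method of birth control or remain abstinent during the study". It attaches no date or window to the test.

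Section 5.1.2 places the test at screening: "If all other criteria are met, a blood sample will be drawn to screen for pregnancy (in female subjects", together with infection and routine safety bloods. Once those are acceptable, subjects are "scheduled for enrollment and Visit 1 as appropriate for any medication washout period required in the exclusion criteria". No maximum interval is given there or elsewhere. The Table 1 footnote (5.4) agrees on timing: CBC and CMP at several visits, "as well as HBV, HCV, HIV, tuberculosis, and pregnancy (for females if childbearing potential) at screening".

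Section 5.1.3 has the eligibility criteria reviewed again, after which "subjects may proceed with visit 1 on the same day if they continue to meet criteria". It names no test. Section 5.1.4 states "Visit 1 will be performed at OHSU for all subjects". The only blood it names is for one purpose: "Blood will be drawn for measuring levels of inflammation". The first guselkumab injection follows at the same visit. The baseline laboratory work in 8.5 does not include a pregnancy test either.

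Other provisions bear on the risk. In 5.1.2, "Contraception method will also be recorded". Visit 1 includes an interval history and a review of systems (5.1.4). Pregnant women are not to be enrolled (4.4). A pregnancy leads to withdrawal (8.4.3) and to stopping study drug (8.7.1).

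**The concern.** Pregnancy is a bar to entry, yet the plan checks it by test only at a visit that may come well before dosing. For any subject who needs a washout, 5.1.2 itself foresees a wait between the blood draw and Visit 1. A negative result from before that wait says nothing about a conception during it.

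What is at stake is fetal exposure to a drug whose fetal risk 8.6 describes as unknown. That section also reports no harm so far and no adverse findings in animals. The issue is therefore an exclusion left unverified at the moment it matters, not a likely known harm. The plan treats such exposure as important: 8.4.2.1 lists it among events needing expedited reporting or safety evaluation, and 8.4.3 requires pregnancies to be reported within 24 hours.

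**Working it through.** The plan gives no figure to reproduce. The check has two parts.

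**1. Does any step before the first dose require a new test?**

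- Screening (5.1.2): test required.
- Enrollment (5.1.3): criteria reviewed again, no test named. Because the criterion in 4.1 is undated, the screening negative still satisfies it on paper.
- Visit 1 (5.1.4): history, examination, biopsies, saliva, blood for inflammation, first dose. No pregnancy test.
- Table 1 footnote: pregnancy at screening only. Its laboratory weeks do not fully match the grid (it lists week 20, while the grid marks a draw at week 24), so the point rests mainly on 5.1.2 and 5.1.4.

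No step requires one.

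**2. How old can the result be at first dose?**

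Let W be the washout in 4.2 and t the time already elapsed since the last dose of the earlier therapy when the screening blood is drawn. Then

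age at first dose = max(W − t, 0) + scheduling time.

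The plan does not give t or limit scheduling time. I assume three values of t and leave scheduling time out. Days are divided by 7: 60/7 = 8.6 and 90/7 = 12.9.

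| Earlier therapy | W (4.2) | t = 0 | t = W/2 | t ≥ W |
|---|---|---|---|---|
| Prednisone | 2 weeks | 2.0 weeks | 1.0 week | 0 |
| Other systemic therapy, phototherapy | 4 weeks, or 5 half-lives if longer | at least 4.0 weeks | at least 2.0 weeks | 0 |
| Etanercept | 28 days | 4.0 weeks | 2.0 weeks | 0 |
| Infliximab, adalimumab, ixekizumab, alefacept | 60 days | 8.6 weeks | 4.3 weeks | 0 |
| Golimumab | 90 days | 12.9 weeks | 6.4 weeks | 0 |
| Secukinumab | 5 months | 5 months | 2.5 months | 0 |
| Ustekinumab | 8 months | 8 months | 4 months | 0 |
| Rituximab, efalizumab | 12 months | 12 months | 6 months | 0 |

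The last three rows at t = 0 need a woman screened on about the day of her last dose of a long-acting biologic, who then waits out the whole period on that one screening. They are hypothetical upper cases. The gap does not depend on them: an ordinary 4-week washout is enough to make the result out of date.

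Section 4.3 recruits newly diagnosed subjects, who may need no washout, as well as subjects failing other treatment, for whom a washout is a normal route in. The documents do not say how many of the 15 will be women of childbearing potential who wait.

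**The case against.** The best defence has three parts.

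First, 5.1.2 draws blood only when all other criteria are met, and washout is one of the criteria. Read literally, a subject still in washout would not yet be bled, and only scheduling time would remain. But 5.1.2 then schedules Visit 1 around any washout after the bloods are known, which points the other way. Under either reading the interval has no limit. The tension is a fair reason not to present the long intervals as typical.

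Second, the safeguards are real. Women agree to contraception or abstinence, the method is recorded, Visit 1 takes a history and review of systems, subjects proceed only if they still meet the criteria, and a known pregnancy stops treatment. An investigator could read the re-review as asking for current status and choose to retest. This stands as risk reduction. It does not close the gap. History finds a pregnancy that is known or suspected, and stopping rules act once it is known, possibly after exposure. The contraception commitment runs during the study, and the text does not say whether that includes a pre-enrollment washout. No retest is mandatory.

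Third, the documents set no standard requiring a test at dosing, 8.6 reports no harm to date, and the number affected may be zero. This stands too, and it limits how much weight the point carries.

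A reader might infer that women will routinely be dosed on results many months old, or that fetal harm is likely. The documents support neither: the first needs the extreme screening date described above, and 8.6 calls the risk unknown without reporting any harm.

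**Conclusion.** The point holds as a gap in verifying eligibility at the first dose. Exact adherence to the plan allows a woman of childbearing potential to receive guselkumab with no current pregnancy test.

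If screening falls at about the last dose of the earlier therapy, the result would be about 2 weeks old after prednisone, 4 weeks or more after other systemic therapy, phototherapy or etanercept, and about 9 to 13 weeks after the 60- and 90-day biologics. It would be roughly half that if half the washout has passed, and only scheduling time would remain if washout is complete. These ages rest on the assumed screening date and exclude scheduling time.

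The remaining risk is an unrecognised pregnancy despite agreed contraception, in a number of women that may be zero. Power and the primary PASI analysis are not affected. The change is worth making because it is small and makes an existing exclusion checkable when it applies. The absence of tests before the week 4, 12 and 20 doses is a separate clinical question on which this point does not rely.

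**What to change.** In 5.1.4 and Table 1, add a pregnancy test at Visit 1 for women of childbearing potential, and state that a negative result must be available before the first dose.

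The cost is a few lines of protocol wording and one inexpensive test per such woman: at most 15 in the planned sample, plus any replacement subjects allowed by 8.7.2. Visit 1 is already in person for everyone and already includes a blood draw. There are two practical downsides. The result is needed the same day, before dosing, and a positive result could mean a wasted trip for someone who has travelled far.

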5.1.3. Enrollment

The inclusion/exclusion criteria will be re-reviewed and subjects may proceed with visit 1 on the same day if they continue to meet criteria.

5.1.4. Visit 1 / Week-0 (baseline)

Visit 1 will be performed at OHSU for all subjects.

- Study personnel will gather the following information from the subjects and record the results in REDCap:
 - Demographics (sex, gender, race, ethnicity)
 - Current medications
 - Drug allergies
 - Use of alcohol, tobacco, and other substances
 - PRP medical history
 - General medical history and adverse events since screening
 - Family medical history
 - Review of Systems
 - Height and weight
 - Blood pressure
 - Pulse
- Subjects will enter the following information about their disease and medical history via OHSU REDCap survey:
 - DLQI
 - PSSD
 - iPRPASI
- The subject will be clinically examined by an investigator (clinician or research nurse) who will assess the following and record the results in OHSU REDCap:
 - Full body skin exam with documentation of PASI, PGA, PPPGA, and NAPSI
 - Examination of the oral mucosa
 - Heart and lung auscultation
 - Palpation of the cervical, axillary, and inguinal lymph nodes
 - Presence of peripheral edema
- Photographs will be taken using a high-resolution digital camera of all body regions against a dark backdrop to visually record extent of disease. Subjects will assume standardized poses according to published recommendations (*31*), with the addition of focused photographs of the palms and nails.
- Subjects will undergo a punch biopsy (consisting of three adjacent 3 mm punch biopsies, a total surface area equivalent to the size of a 5 mm punch biopsy) from affected skin, performed by an

investigator. One additional 3 mm punch biopsy will be obtained from non-lesional skin as a control if non-lesional skin is available. For consistency, skin of back will be chosen for biopsy if an affected site is available. If back skin is not available, alternate sites in order of preference will include: chest, arm, leg. Location of the biopsy will be carefully documented.

- Blood will be drawn for measuring levels of inflammation
- A saliva sample will be collected for genetic analysis
- The first dose of 100 mg of subcutaneous guselkumab will be administered by trained study personnel while the study subject undergoes teaching for future self-administration.
- Subjects who plan to complete future visits by videoconferencing will receive a scale and sphygmomanometer for future vital sign assessments

5.1.5. Visit 2 / Week-4 (28 days +/- 4 days after last visit)

Visit 2 will be performed at OHSU for all subjects.

- Study personnel will gather the following information from the subjects and record the results in REDCap:
 - Change in medications since the last visit
 - Change in drug allergies since the last visit
 - Change in personal or family medical history since the last visit, including adverse events
 - Weight
 - Blood pressure
 - Pulse
- Subjects will enter the following information about their disease and medical history via OHSU REDCap survey:
 - DLQI
 - PSSD
 - iPRPASI
- The subject will be clinically examined by an investigator (clinician or research nurse) who will assess the following:
 - Full body skin exam with documentation of PASI, PGA, and PPPGA
- Photographs will be taken against a dark backdrop with standardized poses according to published recommendations (*31*), with the addition of focused photographs of the palms and nails.
- Subjects will undergo a punch biopsy (consisting of three adjacent 3 mm punch biopsies, a total surface area equivalent to the size of a 5 mm punch biopsy) in the same body region as the first documented biopsy (back, chest, arm, or leg)
- The second dose of 100 mg of subcutaneous guselkumab will be administered by the subject with observation and teaching from study personnel.
- Blood will be drawn for monitoring the CBC, CMP, and measuring levels of inflammation

